3.2.2. Secondary and Exploratory Target Variables

Efficacy

- Proportion of responders in the 0.5 g/kg and 2.0 g/kg NewGam arms at Week 24 relative to baseline at Week 0 compared to the 1.0 g/kg arm, based on the adjusted INCAT disability score
- Proportion of responders in the 0.5 g/kg and 2.0 g/kg NewGam arms at Week 24 relative to baseline at Week 0 compared to the 1.0 g/kg arm, based on the grip strength (Martin Vigorimeter) using the previously published minimum clinically important difference (MCID) cut-off of 8 kPa
- Proportion of responders in the 0.5 g/kg and 2.0 g/kg NewGam arms at Week 24 relative to baseline at Week 0 compared to the 1.0 g/kg arm, based on the I-RODS scores using the MCID concept related to the varying standard errors (MCID-SE) as recently demonstrated (please refer to protocol)
- Time to first confirmed worsening on the adjusted INCAT disability scale by at least 1
 point or more from the value at Baseline
- Mean change from Baseline (Week 0) to Termination Visit in
 - grip strength of both hands (assessed by Martin Vigorimeter)
 - Inflammatory Rasch-built overall disability sum score (I-RODS using the concept of MCID-SE as recently reported; Appendix 1) and number of improvers
 - sum of the distal evoked amplitude of 4 right sided and 4 left sided motor nerves (peroneal, tibial, ulnar and median)
 - Pain Intensity Numeric Rating Scale (PI-NRS)
- Time to first confirmed worsening on the I-RODS scale
- o Time to 1 point decrease (improvement of disability) in adjusted INCAT disability score
- Time to decrease in I-RODS scores
- o Mean change from baseline (Week 0) to Termination Visit in:
 - modified Fatigue Severity Scale (FSS)
 - SF-36 Health Survey physical composite score (PCS), mental composite score (MCS) and their 8 health domains
 - Additional nerve conduction studies (NCS) analyses (e.g. individual nerve analysis)
- o For MRC the following will be done:
 - Time to decrease in MRC sum score to or below baseline value after temporary improvement (increase)
 - mean change from baseline (Week 0) to Week 12 and to Termination Visit
 - number of improvers by at least 4 points from baseline (Week 0) to Week 12
 and to Week 24

Safety:

- o Throughout the entire 24-week Dose-evaluation Phase:
- Occurrence of all adverse events (AEs)
- Short term tolerance parameters including vital signs
- Physical/neurological examination

 Laboratory parameters: Serum IgG, hematology, clinical chemistry, urinalysis, pregnancy test, and tests for viral safety

4. Study Methods

4.1. Overall Study Design and Plan

Study NGAM-08 is designed as a prospective, double-blind, randomized, multicenter phase III study. The rationale for conducting this study is to confirm the published clinical results obtained with the 1.0 g/kg dosing in order to apply for market authorization of NewGam, and to evaluate different dosing options on both sides of the standard dose with respect to efficacy and safety.

Patients will be screened for eligibility and, if eligible, thereafter have to decrease their current medication (Immunoglobulins by 25% from infusion to infusion or corticosteroids as per the discretion of the Investigator at a rate to expect study entry within 6-12 weeks) for a maximum of 12 weeks (Wash-out Phase). Only patients who deteriorate in this phase, i.e. active patients who need treatment, will be randomized 1:2:1 between three different dosages of NewGam (0.5 g/kg, 1.0 g/kg or 2.0 g/kg NewGam), and enter the Dose-Evaluation Phase.

[figure not shown]
The two allowed types of treatment prior to enrollment – Immunoglobulins or Corticosteroids – will be considered as strata in a stratified block design randomization with fixed block size. An electronic IWRS tool will be used to realize the randomization ratio of 1:2:1 with respect to the dosage groups, in each of the strata independently.

During the 24-week Dose-evaluation Phase all patients will first receive an initial loading dose of 2.0 g/kg NewGam, followed by 7 maintenance dosages of 0.5 g/kg, 1.0 g/kg or 2.0 g/kg NewGam every 3 weeks as they were randomized to.

Patients not deteriorating in the 12-week Wash-out Phase will not be enrolled into the ProCID study as they are not having active CIDP.

In addition the following rescue treatment option will be available: two consecutive infusions of 2.0 g/kg NewGam at 3-week intervals for all patients in the 0.5 and 1.0 g/kg NewGam arms who are either stable at Week 6 or deteriorate after Week 3 and before Week 18. Patients in the 2.0 g/kg NewGam arm will drop-out if they are stable at Week 6 or deteriorating after Week 3 and before Week 21.

4.2. Selection of Study Population

The study population consists of patients of both sexes, ≥ 18 years of age, with documented diagnosis of CIDP by a neurologist specialized/experienced in neuromuscular diseases. Eligible patients need to fulfill the definite or probable EFNS/PNS criteria for CIDP, and have to have an adjusted INCAT disability score between 2 and 9 at screening (a score of 2 has to be exclusively from leg disability).

Please refer to the protocol for the complete list of all eligibility criteria.

5. Sequence of Planned Analyses

5.1. Interim Analyses

No interim analysis is planned in this study.

5.2. Final Analyses and Reporting

Once the last patient has completed the study, data validation will be completed and the database will be locked according to the applicable standard operating procedures. This process includes (blinded) data review, medical coding and review, the identification and classification of any protocol deviations as detailed in section 7, and thus the patient disposition with respect to the analysis populations. After completion of all these procedures and the finalization of the statistical analysis plan, the formal database lock can be conducted. Only after that the blind will be broken, and the individual treatment assignment will be added to the clinical database for analysis.

All final, planned, analyses identified in the protocol and in the SAP will then be performed.

Key statistics and study results will be made available to the study team following database lock and prior to completion of the final CSR by means of tables, figures and listings.

Any, post-hoc, exploratory analyses completed to support planned study analyses, which were not identified in the final SAP, will be documented and reported in appendices to the CSR. Any results from these unplanned analyses will also be clearly identified in the text of the CSR.

6. Sample Size Determination

The sample size calculation is based on the proportion of responders in the 1.0 g/kg dose group. This dose regimen is the currently most commonly used for maintenance IGIV doses in CIDP. Recent experiences with this dosing regimen are available from the ICE study and the PRIMA trial (please refer to the protocol for more details). In both of these studies, the lower confidence limit of the 95% Wilson-Score confidence interval for the proportion of responders (*R*) was 42% if rounded to the nearest integer, and thus we have also chosen 42% as the threshold for the following pair of hypotheses for evaluation of the primary endpoint:

[figure not shown]
 H_0 : R < 0.42

 $H_1: R \ge 0.42$

This will be tested by comparing the lower limit of the 95% Wilson-Score confidence interval for the observed proportion of responders with the pre-defined threshold of 0.42.

We estimate the true percentage of responders in CIDP patients treated with NewGam as 60%. This corresponds to the 60.7% of responders observed in the PRIMA study, but is higher than the outcome in the ICE (54.2%), that in the opinion of many experts underestimates the true percentage of responders.

We applied these parameters to a computer simulation realized in SAS to determine the statistical power associated with various group sizes:

Power to show that the lower 95% confidence limit for the responder rate is above 42%, assuming a real response rates of 60%

To achieve a power of at least 80%, a minimum of 62 evaluable patients in the 1 g/kg dose group will be needed; to account for possible dropouts we plan to enroll 70 patients into this group.

In order to allow for the comparison between dose groups, we plan to enroll half the same number of patients also into the other groups (0.5 g/kg and 2.0 g/kg), resulting in a total of 124 evaluable patients, and an enrollment target of 140 patients overall.

6.1. Patient Replacement Policy

Only in case of a withdrawal portion in excess of 10%, patients will be replaced, unless the planned number of patients in the respective dose group has been achieved already. A replacement patient will be assigned to the same treatment group as the withdrawn patient.

Patients withdrawn from the study because of safety reasons will not be replaced.

6.2. Premature Termination of the Study

If early termination of the study becomes necessary, the sponsor and the investigator will ensure that adequate consideration is given to the protection of the patients' interests. Premature termination will be notified in accordance with applicable regulatory requirements. Early termination might concern the study as a whole or individual centers. In any case the blind will be maintained until all database locking procedures are completed and the database has been locked; this includes finalization of the statistical analysis plan, which will be adapted to cover any issues arising from the premature termination.

7. Analysis Populations

The following populations will be considered for the statistical analysis:

The **safety set (SAF)** will include all randomized patients who received at least part of one infusion of IMP.

The **full analysis set (FAS)** is defined according to the intention-to-treat principle, and will include all patients of the SAF for whom any data was collected post infusion of IMP. Every treated subject will be considered in the analysis according to his randomized treatment/dose assignment.

The **per-protocol set (PPS)** – being a subset of the FAS — will exclude patients with significant protocol deviations, which may have an impact on the evaluation of the primary study outcome parameter(s). This is the set of patients who participated in the study as intended and for whom the primary efficacy endpoint can be evaluated as planned.

All protocol deviations documented during the conduct of the study or identified at the data review process prior to DB lock will be reviewed and classified as minor or major and with respect to its effect on the planned analysis. Only major protocol deviations with the potential to significantly affect the study results or to invalidate the interpretation of the data obtained will lead to exclusion of patients from the PP set. This classification of protocol deviations is the joint responsibility of the clinical study manager, the study statistician, and Octapharma's responsible medical expert, and will be performed and documented before the database is locked and the statistical analyses are performed.

The analysis of safety will be based on the safety set.

The evaluation of primary objective(s) will be performed for the FAS (intention-to-treat analysis) and for the PPS (per-protocol analysis). The ITT analysis is considered to be the most relevant, and will be presented first in the statistical report.

The evaluation of secondary objectives will be performed for the FAS, and in addition for the PPS in case the two populations differ by more than 5%.

7.1. Subgroups

In addition to combined presentations over all strata, evaluation of the primary endpoint will be presented for each randomization stratum (prior treatment with Immunoglobulins or Corticosteroids) separately to facilitate the identification of noteworthy differences in the clinical responses between these two groups.

The different CIDP variants eligible for enrollment, such as Multifocal Acquired Demyelinating Sensory And Motor Neuropathy (MADSAM) or pure motor CIDP, will be compared with respect to dose group and proportion of response as well.

Additional analyses, such as logistic regression or ANCOVA, will be deployed for primary and secondary endpoints to further examine differences between subgroups in an exploratory manner. The ANCOVA models will also be used for least square means calculation including 95% confidence intervals in various subgroups (see section 10.2).

8. General Issues for Statistical Analysis

Descriptive summaries will be presented for each of the primary, secondary and exploratory variables. In general, summaries will be completed for all patients overall and by dose group, and the data will be presented by means of standard summary statistics according to the different types of data:

- Binary data (whether or not an event has occurred): counts and proportions
- Count data (the frequency of an event in a set time period): rate (count per unit time)
- Continuous data (measurements on a continuous scale, including quasi-continuous variables): arithmetic mean, standard deviation, median, minimum, maximum
- Scales data (Ordinal and Non-ordinal): absolute and relative frequencies
- Time-to-event data (how long it takes to observe the outcome of interest: time to event or last evaluation (censored data in case patients are lost to follow-up) and event rate). These parameters might not be tabulated separately, but can be included as an inset into a Kaplan-Meier plot of the product-limit survival function estimates.

Additional descriptive and exploratory statistics, such as geometric means, quartiles or confidence intervals, are included as appropriate. If not mentioned otherwise, confidence intervals are to be understood as two-sided, 95% confidence intervals.

In general the denominator for calculating percentages will be the total number of patients in the analysis population unless otherwise specified.

8.1. Analysis Software

Statistical analyses will be performed using SAS Software version 9.1 or later.

8.2. Withdrawals

Patients who withdraw from the study prematurely will be considered in all data presentations for which they contribute data; in particular patients who fail to perform an INCAT evaluation at week 24 will be considered to be non-responders in the analysis of the primary endpoint in the FAS.

8.3. Handling of Missing Data

In general, missing data will not be imputed, and all data derivations will be based on observed values only; exceptions are:

In case of missing body weight, the last available weight measurement will be used for calculating the dose per kg bodyweight (last observation carried forward (LOCF)).

Because the overall disability sum score (I-RODS) cannot be calculated if not all activities are evaluated, missing items will be replaced by the latest available score of the same activity (LOCF).

If missing values occur in the confirmatory analysis of the primary endpoint in the FAS, they will be imputed by worst observed values, i.e. the patient concerned will be analyzed as non-responder.

No analyses of the patterns of missing data will be done.

For adverse events the following will be applied:

An Adverse Event (AE) is defined as treatment-emergent, if first onset or worsening is after start of the first infusion of *NewGam*.

If the start date and time of an AE are partially or completely missing, the AE will be assumed to be treatment-emergent if it cannot be definitely shown that the AE did not occur or worsen after start of the first infusion of *NewGam*. Missing dates and times will not be replaced.

For medications the following will be applied: A medication will be assumed to be concomitant if it cannot be definitely shown that the medication was not administered after start of the first infusion of *NewGam*. Missing dates will not be replaced.

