
 • Time to first confirmed worsening on the adjusted INCAT disability scale by at least 1 point from the value at baseline (Week 0) • Mean change from baseline (Week 0) to Termination Visit in 
 ○ grip strength of both hands (assessed by Martin Vigorimeter) ○ Inflammatory Rasch-built overall disability sum score (I-RODS using the concept of MCID-SE as recently reported; Appendix 1) and number of improvers ○ sum of the distal evoked amplitude of 4 right sided and 4 left sided motor nerves (peroneal, tibial, ulnar and median) ○ Pain Intensity Numeric Rating Scale (PI-NRS) • Time to first confirmed worsening on the I-RODS scale • Time to 1 point decrease (improvement of disability) in adjusted INCAT disability score • Time to decrease in I-RODS scores 
Exploratory
 
 • Mean change from baseline (Week 0) to Termination Visit in: 
 ○ modified Fatigue Severity Scale (FSS; 7-item scale from 0-21 points; see Appendix 2) ○ number of improvers by at least 4 points in the MRC sum score (according to the universal rule of minimal clinical important difference) ○ SF-36 Health Survey physical composite score (PCS), mental composite score (MCS) and their 8 health domains (see Appendix 3) ○ additional NCS analyses (e.g. individual nerve analysis) • Time to decrease in MRC sum score to or below baseline value after temporary improvement (increase) 
Safety (throughout the entire Wash-out and Dose-evaluation Phases):
 
 • Occurrence of all adverse events (AEs) • Short term tolerance parameters including vital signs • Physical/neurological examination • Laboratory parameters (hematology and clinical chemistry) and tests for viral safety 	
Summary of Study Procedures and Statistical Analysis Plan:	
Study Procedures:	
Disability will be assessed by the adjusted INCAT score and the I-RODS at each visit.	
Pain will be assessed by the PI-NRS at each visit.	
Impairment will be assessed by the grip strength at each visit, MRC sum score and the modified FSS (Fatigue Scale) at Screening, Week 0, Week 12 and Termination Visit.	
Quality of life (SF-36) will be measured at Screening, Week 0, Week 12, and at Termination Visit.	

Name of Sponsor/Company: Octapharma Pharmazeutika Produktionsges.m.b.H., 1100 Vienna, AT	

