FLOWCHART

	Screening	Wash-out Phase ¹	Dose-evaluation Phase ²								
	Visit 1 Week -15	Week -12 to 0	Visit 2 Week 0	Visit 3 Week 3	Visit 4 Week 6	Visit 5 Week 9	Visit 6 Week 12	Visit 7 Week 15	Visit 8 Week 18	Visit 9 Week 21	Termination visit Week 24
Informed consent	X										
Medical history	X										
In-/Exclusion criteria	X		X								
Randomization/Enrollment			X								
Concomitant medication		X ¹⁰	X	X	X	X	X	X	X	X	X
Adverse events		X ¹⁰	X	X	X	X	X	X	X	X	X
Physical/neurological examination	X		X				X				X
ECG	X										
Clinical chemistry ³ ; Hematology ⁴	X		X	X	X	X	X	X	X	X	X
Serum IgG ⁵			X	X	X	X	X	X	X	X	X
Urinalysis ⁶	X										X
Pregnancy test ¹¹	X										
Viral marker ⁷	X		X								X
PGIC scale			X								
Adjusted INCAT score; I-RODS score, PI-NRS	X		X	X	X	X	X	X	X	X	X
Grip strength	X		X	X	X	X	X	X	X	X	X
MRC sum score	X		X				X				X
Modified FSS	X		X				X				X
Nerve Conduction Studies	X		X				X				X
SF-36 Health Survey	X		X				X				X
Vital signs ⁸ ; Weight	X		X	X	X	X	X	X	X	X	
Study drug infusion			X ⁹	X	X, [X ^{12,13}]	X, [X ^{12,13}]	X, [X ¹²]	X, [X ¹²]	X, [X ¹²]	X, [X ¹²]	

¹ May last up to 12 weeks (until deterioration): Selection of active patients requiring treatment after dosage reduction

² Infusion visits take 2 days

³ Clinical chemistry: Na⁺, K⁺, glucose, ALAT/ALT/GPT, ASAT/AST/GOT, LDH, total bilirubin, BUN (blood urea nitrogen) or urea, creatinine, albumin, serum IgG

⁴ Hematology: Hematocrit, hemoglobin, CBC with differential

⁵ Serum IgG to be determined prior to infusion

⁶ Urinalysis: Protein, pH, glucose, ketones, leukocytes, hemoglobin and blood

⁷ Viral Markers: HIV, HBV and HCV

⁸ Vital signs: Pulse, blood pressure, respiratory rate and temperature

⁹ Loading dose of 2.0 g/kg NewGam

¹⁰ Only for patients on immunoglobulin treatment visiting the site for infusions

¹¹ Pregnancy test should only be done in women of childbearing potential (WOCBP). Pregnancy test is mandatory at Visit 1. At Visit 2, 3, 4, 5, 6, 7, 8, 9 and Termination Visit a pregnancy test should be performed only if required by local regulations.

¹² Two consecutive 3-weekly infusions of 2.0 g/kg NewGam only for patients on 0.5 or 1.0 g/kg NewGam who deteriorate after Week 3 and until Week 18

¹³ Two consecutive 3-weekly infusions of 2.0 g/kg NewGam only for patients on 0.5 or 1.0 g/kg NewGam being stable by Week 6

Signature of the Coordinating Investigator

This study is intended to be conducted in compliance with the protocol,

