3.2 Overall Study Design and Plan

ProCID study is planned to start in Q1 2017 and be completed by Q4 2019, corresponding to a total duration of 30 months. The enrollment period is projected to last approximately 20 months.

ProCID study will be a prospective, parallel group, double-blind, randomized, multicenter, Phase 3 study in a minimum of 140 adult patients of both genders with definite or probable CIDP according to the EFNS/PNS Criteria.[12] As CIDP is a rare disease, about 45 sites are projected to participate worldwide, with emphasis on Eastern European countries, and projecting about 3-4 patients for each study site.

Data from the 1.0 g/kg arms in the ICE [24] and PRIMA [25] trials will be used as historical controls.

Patients will be screened, and if eligible for this trial, their current medication will be reduced in a predefined standard manner (immunoglobulins: 25% at each sequential infusion or corticosteroids as per the discretion of the Investigator at a rate to expect study entry within 6-12 weeks) for a maximum of 12 weeks. Only patients who deteriorated in this phase, i.e. active patients who demonstrate needing treatment (i.e., patients whose overall status worsened according to the Patients' Global Impression of Change² (PGIC) scale PLUS are either increasing on the INCAT by at least 1 point OR decreasing at least 8 kPa on grip strength in

² PGIC, a 7-point scale on which patients rate change in overall status since start of Wash-out Phase (1-3 = improved, 4 = no change, 5-7 = worsened).

one hand OR at least reaching the I-RODS MCID-SE cut-off of -1.96 or less), will be randomized 1:2:1 between three different maintenance dosages of 0.5 g/kg, 1.0 g/kg or 2.0 g/kg NewGam in the Dose-evaluation Phase.

Patients not deteriorating in the 12-week Wash-out Phase will not be enrolled into the ProCID study as they are not having active disease. Their treating physician will decide when and which treatment will be started in these patients as part of the health system's standard of care foreseen for CIDP patients.

[figure not shown]

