6.1.2 Procedures During the Wash-out Phase of the Study

Eligible patients will have to enter a Wash-out Phase of up to 12 weeks, i.e., they have to decrease their current medication (immunoglobulins or corticosteroids; see Section 3.2). In this Phase the medication will successively be reduced until the patient deteriorates.

For patients on corticosteroids, no scheduled or required study evaluations/visits will take place during the Wash-out Phase. However the patients must inform the investigator whenever they notice any symptom of disease worsening at any time during the Wash-out Phase and must come to the site for assessment of deterioration. If deterioration cannot be confirmed, the Wash-out Phase will continue.

Patients on immunoglobulin treatment will have to visit the study site (e.g. IGIV every three weeks) for their infusions. Thus, from these patients concomitant medications and AEs will be recorded.

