9.2.4 Handling of Missing Data

In general, missing data will not be imputed, and all data derivations will be based on observed values only. Only in case of missing body weight, the last available weight measurement will be used for calculating the dose per kg bodyweight (last observation carried forward).

If missing values occur in the confirmatory analysis of the primary endpoint in the FAS, they will be imputed by worst observed values, i.e. the patient concerned will be analyzed as non-responder.

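### SAP 8.3 lets a missing Week 0 I-RODS item take the Screening score from before the required deterioration, which in expectation overstates baseline and understates I-RODS gain for the patients affected

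*SAP*

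**What the plan says.** **Imputation rule.** SAP 8.3 explains that the I-RODS sum score needs every activity to be rated, so "missing items will be replaced by the latest available score of the same activity (LOCF"). It sets no limit on how old the donor score may be or how many items may be filled, and does not treat Week 0 separately. The same section plans no analysis of missing-data patterns.

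**Protocol rule.** Protocol 9.2.4 is narrower on carry-forward: "Only in case of missing body weight, the last available weight measurement will be used". Its only other imputation counts a missing primary outcome as non-response. The SAP document history does not list I-RODS item imputation among the changes.

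**Schedule.** The protocol synopsis states that disability "will be assessed by the adjusted INCAT score and the I-RODS at each visit". The flowchart row "Adjusted INCAT score; I-RODS score, PI-NRS" is marked at Screening, blank for the Wash-out Phase, and marked again from Week 0. Protocol 6.1.2 says that for corticosteroid patients "no scheduled or required study evaluations/visits will take place during the Wash-out Phase". For immunoglobulin patients attending for infusions it says "Thus, from these patients concomitant medications and AEs will be recorded".

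**Selection.** Protocol 3.2 randomizes as follows: "Only patients who deteriorated in this phase, i.e. active patients who demonstrate needing treatment". The criterion is a worsened PGIC plus any one of an INCAT increase, a grip-strength fall, or "at least reaching the I-RODS MCID-SE cut-off of -1.96 or less".

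**Use of Week 0.** Week 0 is the reference for I-RODS response (MCID-SE of 1.96 or more at Week 24 without rescue, SAP 8.4), for I-RODS worsening and time-to-event endpoints, and for the ANCOVA of change, where it is also the covariate (SAP 10.2).

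**The concern.** Carrying a value forward is least safe across an interval in which the outcome is known to move. Here the plan carries items across the Wash-out Phase, where treatment is tapered and decline is a condition of entry. Since a higher I-RODS score is better, an item taken from Screening will on average be better than the patient's true Week 0 answer. The baseline is then too high and the measured gain to Week 24 too small. Some patients who improved may miss the 1.96 cut-off, and the I-RODS deterioration after Wash-out tabulated under SAP 9.3 looks smaller than it was.

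A related problem arises at Week 3. A missing item there takes the Week 0 answer, given before the loading dose, which can delay the recorded time to I-RODS improvement.

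No planned output would reveal how many Week 0 scores contain Screening items.

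**Working it through.** The plan states no figure for I-RODS missingness or imputation, so there is nothing to reproduce on this point. The sample size of 62 evaluable patients in the 1.0 g/kg arm rests on INCAT and is not involved.

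**Step 1: age of the donor score.** Screening lasts about 3 weeks and Wash-out up to 12 (Protocol 6.2.1), so a Screening item can be about 3 + 12 = 15 weeks old at Week 0.

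**Step 2: expected bias.** Let f be the share of Week 0 items missing at random, D the fall in I-RODS from Screening to Week 0, and G the true gain from Week 0 to Week 24.
- Overstatement of baseline = f × D.
- Share of the gain lost = f × D / G.

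If the patient regains what was lost (D = G), the share lost is simply f. The item count is not visible in the documents (Appendix 1 is not reproduced), so it is an assumption:

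| Missing items | 20 items | 24 items | 30 items |
|---|---|---|---|
| 2 | 10% | 8% | 7% |
| 4 | 20% | 17% | 13% |
| 6 | 30% | 25% | 20% |

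If D = 0 on I-RODS, the bias is zero. If the whole Week 0 form were missing (f = 1) with D = G, the gain would vanish.

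**Step 3: raw-score check.** Simulation with 24 items scored 0 to 2:
- D = 3 points, true gain 2.7: 1, 2 or 4 missing items lower the mean gain by 0.13, 0.25 or 0.50 points. The formula gives 3 × 1/24, 3 × 2/24 and 3 × 4/24, which agrees.
- D = 6 points, true gain 5.4: the reductions are 0.25, 0.50 and 1.00 points.

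**Step 4: effect on response.** Simulation of affected patients with the same assumed scale, mean baseline 0 logits, Wash-out losses of 1 to 2 logits and 2 to 6 missing Week 0 items:
- Carry-forward from Screening cuts mean gain by about 7 to 24% and the response rate by about 5 to 24 percentage points.
- Rasch scoring from the Week 0 answers alone leaves mean gain unbiased and lowers the response rate by only 1 to 7 points, because the standard errors are larger.

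**Step 5: trial level.** The effect on an arm's response rate is the share of its patients with incomplete Week 0 forms, times the Step 4 figure. That share is not given. If it were 5%, the arm's rate would fall by 0.05 × 5 = 0.25 to 0.05 × 24 = 1.2 points. If it were 10%, by 0.5 to 2.4 points.

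**The case against.** **The direction is not certain for each patient.** This stands. A patient can qualify on INCAT or grip strength with I-RODS unchanged, and the bias is then zero. It would be wrong to infer from the entry rule that every randomized patient fell on I-RODS. The upward bias is an expectation over patients.

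**A later score than Screening may exist.** This stands in part. Protocol 6.1.2 has corticosteroid patients come in during Wash-out for assessment of deterioration, and Wash-out continues if it is not confirmed. An I-RODS score from such a visit could be the donor. None is scheduled, however, so Screening is the default source.

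**Classifications would not change.** In noise-free cases (baselines of -1, 0 and 1 logit, thresholds of ±0.7, and MCID-SE assumed to be the difference over the root of the summed squared standard errors, because the SAP formula is not visible), full recovery of a 2-logit loss drops from 3.1–3.3 to 2.4–3.0 and is still a response. A 1-logit recovery, at about 1.65, is a non-response even without carry-forward. That holds only for those fixed cases. With ordinary response noise, patients scatter around the cut-off, and Step 4 shows that the rate falls.

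The same cases do undercut a stronger inference, that stability would be read as worsening. A stable patient reaches only -0.13 to -0.83, well short of -1.96, and the endpoint requires confirmed worsening.

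**Planned inference is barely touched.** This largely stands. Week 0 items are recorded before infusion and under blinding, so missingness should not depend on dose. The ANCOVA adjusts for baseline, and the I-RODS comparisons are descriptive or exploratory. A reader might infer biased dose comparisons or a weakened primary result; the documents support neither.

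**The SAP is open about the rule.** It lists the rule as an exception and gives a reason, and the protocol leaves analysis details to the SAP. What is missing is a statement that it differs from protocol 9.2.4.

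**Conclusion.** The point holds as a limited one. The rule, the schedule and the entry criterion together make the Screening score the default donor for a missing Week 0 I-RODS item, and the resulting baseline is too high in expectation. Among patients with 2 to 6 missing Week 0 items, I-RODS gain is understated by about 7 to 24% and response by about 5 to 24 percentage points. These figures rest on an assumed 24-item scale scored 0 to 2, items missing at random, and Wash-out losses of 1 to 2 logits.

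Patients with complete Week 0 forms are unaffected. The rate of incomplete forms is not given, so no trial-level figure can be claimed, and the error runs against the product. What is at risk is the within-arm description of I-RODS benefit, a secondary result. This is a worthwhile clarification and does not threaten the trial's main conclusion.

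**What to change.** Amend SAP 8.3, before the blind is broken, as follows.

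1. Screening (pre-Wash-out) items are not carried into Week 0.
2. A Week 0 form with missing items is scored from the items answered at that visit: either a Rasch person location and standard error from those items, or a prorated sum score. State which, and the minimum number of answered items. This has to replace the present statement that an incomplete form cannot be scored.
3. A patient whose Week 0 form falls below the minimum is left out of the I-RODS change and response analyses. SAP 8.4 needs a matching line, because its catch-all would otherwise make such a patient a non-responder, a larger bias in the same direction.
4. Week 3 forms use the same within-visit scoring, so that pre-treatment Week 0 items are not carried past the loading dose and Week 3 still has a rule.
5. Report the number of Week 0 scores with missing items, by dose group.
6. State that I-RODS item imputation departs from protocol 9.2.4.

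The cost is a few sentences and one table row, slightly larger standard errors for partial forms, and possibly a few patients without an I-RODS baseline. Sample size, the primary analysis and data collection do not change.
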